Imaging: ¹¹C-ER176 will be produced in full accordance with GMP requirements in the Mayo Clinic Cyclotron Facility. All PET/CT imaging will take place in the PET/CT Molecular Imaging Research Center on [REDACTED] of Mayo Clinic. PET/CT imaging will be performed on a state-of-the art digital PET/CT system (Siemens Biograph Vision 600, Siemens Healthineers). This system utilizes silicon photomultiplier PET detectors to attain a spatial resolution of 3.7 mm, a timing resolution of 210 picoseconds and a sensitivity of 16 cps/kBq over a 26-cm axial field-of-view.

Prior to imaging, a pregnancy test will be administered to women of child-bearing potential. The subject will void their bladder and an intravenous (IV) line will be placed in an arm for administration of ¹¹C-ER176. Participants will be given small amount of water (≤ 250 ml) immediately before the PET scan to allow gastric distension. The subject will be positioned supine on the imaging table with their head in a head-holder. Participants will be monitored visually and intermittently for adverse events during injection.

The participants will have a low-dose, non-gated, non-contrast-enhanced, free-breathing CT from the orbits to upper thigh for attenuation correction (CTAC) and anatomic co-localization. Immediately following the start of the PET scan, 518 MBq (14 mCi) (range 370-666 MBq; 10-18 mCi) of ¹¹C-ER 176 will be administered intravenously followed by a saline flush. The first 6 min of PET scanning will be a dynamic acquisition over the heart for measurement of the bolus phase of an input function (IF) which represents the amount of ¹¹C-ER176 in blood supplying tissue as a function of time. Next, 8-10 static images will be acquired sequentially by automatically shuttling the imaging table and scanning the patient from upper chest through abdomen, which will include the heart for late phase of the IF in multiple passes. A whole-body PET scan from the orbits to upper thigh will then be acquired at the end (60-min post injection). All PET data will be reconstructed with fully-3D iterative reconstruction algorithms that include corrections for attenuation (using the CTAC scan), scatter, randoms, dead time, decay and normalization.

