- 1) Survey questionnaires: Questionnaires pose no more than minimal risk to the participants. There is a potential for perception of privacy intrusion. However, the subjects have the right to refuse to answer any of the questions or stop at any time, and there is no penalty for refusing to participate. No complications have been recorded. The proposed questionnaires are validated, widely used, and were received well by the participants.
- 2) ¹¹C ER 176 PET/CT scan: PET scans and the tracers used are generally safe. In a recent study, no adverse or clinically detectable pharmacologic effects were observed with ¹¹C-ER176 for any of the 17 subjects
- 3) EUS-guided core biopsy: Mild self-limiting serosal bruising and/or localized hematoma formation at the sites of EUS biopsies. Other standard risks of an upper endoscopy include pain (abdominal and throat), aspiration and extremely rarely, death. Serious risk of bleeding and frank perforation is rare (<1 in 1000).

3. Potential Benefits of the Proposed Research to the Subjects and Others

The proposed research has the potential to remarkably enhance our understanding of visualizing immune dysregulation in the gastric muscle of patients with diabetic gastroparesis. This will have a downstream effect of identifying immune dysfunction in other GI conditions. Broadly, this can revolutionize assessment of inflammatory milieu in areas that are not easily or safely amenable for a biopsy. As of now, there likely will not be a direct benefit to the gastroparesis patients as we still do not have clear therapies to target immune dysfunction in gastroparesis. Given the anticipated mechanistic insights to the participants in this research proposal, and to others with diabetic gut dysfunction, the benefits outweigh the risks.

4. Importance of the Knowledge to be Gained

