The proposed research has the potential to develop a new approach to diagnose immune dysregulation in diabetic gastroparesis, a disorder with unmet clinical need. Specifically, this project is aiming to determine if a special radio ligand ¹¹C ER 176 based PET/CT imaging can detect activated macrophages in the gastric muscle of patients with diabetic gastroparesis. Additionally, these results will be validated using actual assessment of gastric muscle tissue to determine cellular markers that associate with pro- or anti-inflammatory macrophages. This study will open a novel paradigm for assessment of immune dysregulation in the GI tract which will have utility for a broad range of GI conditions. This pilot and feasibility proposal will generate novel preliminary evidence for future investigations in this area and treatment trials. The risks to the participants are fairly low with questionnaires, PET/CT scan and EUS with biopsies which are safe procedures. Given the repertoire of the PI and study team in conducting mechanistic, endoscopic and imaging studies of this nature as well as the precautions taken to minimize discomfort or adverse effects, the overall risk of this study is fairly low. There is a high likelihood (e.g., investigator team's record and expertise, validated methods) of obtaining meaningful, useful information for the proposed aim.

5. Data and Safety Plan

Subject Safety: Adverse Events

Adverse Event Grading

Attribution scale: An adverse event is defined as either an expected side effect that is of a serious nature, or an unexpected side effect regardless of severity. All events will be graded as to their attribution (unrelated to protocol: possibly, probably, or definitely related to protocol). Any event that is reported to either the PI or his designated research associates by the subject or medical staff caring for the subject and which meets the criteria will be documented as such.

Expected risks: These risks will be addressed in the protocol and consent form. The expected risks include:

- Loss of confidentiality through unauthorized release of private medical information. This is unlikely since all data are collected in electronic form and access is protected by user identification ID.
- Questionnaires pose some risk of causing emotional distress but these are validated and widely used questionnaires which are typically well received.

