- ¹¹C ER 176 based PET/CT imaging is generally safe and no adverse effects were noted in published studies. However, there is radiation exposure which can be harmful. Additionally, there could be intolerance to the IV injection of radio ligand.
- EUS with core gastric biopsies are generally low risk, especially with an advanced endoscopist like [name] who will perform this procedure on all proposed participants. Adverse effects include abdominal pain, bleeding, and perforation. Rarely, these adverse events can lead to sepsis and death. However, the probability of a serious adverse event is 1 in 2000 or less, making the procedure quite safe.

Plan for Reporting both Anticipated and Unanticipated Adverse Events.

Any adverse event that is reported generates a report, which will be submitted to the Mayo Clinic IRB. The report will include a description of the event, when and how it was reported, as well as any official chart records or documentation to corroborate the event or the reporting of the event. All adverse events will be graded as mild, moderate, or severe. Any severe and/or unanticipated adverse event will be reported within 24 hours to the IRB. All other adverse events will be reported in a timely fashion to the IRB, preferably within 2 weeks. All adverse events will be summarized annually and submitted to the IRB.

Subject Safety: Safety review plan and monitoring

Safety Reviews: The PI will review the safety and progress of this study on a quarterly basis.

Annual Review: The PI will review this protocol on a continuing basis for participant safety and include results of the review in the annual progress reports submitted to the IRB. The annual report will address: (1) whether adverse event rates are consistent with pre-study assumptions; (2) reason for dropouts from the study; (3) whether all participants met entry criteria; (4) whether continuation of the study is justified on the basis that additional data are needed to accomplish the stated aims of the study; and (5) conditions whereby the study might be terminated prematurely.

Data Integrity

Adherence Statement: The DSMP outlined will adhere to the protocol approved by the Mayo Clinic IRB (IRB-C which handles research conducted in the Mayo Clinic CCaTS).

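### Adverse events are actively looked for only during tracer injection and otherwise depend on unsolicited reports under a narrow definition, so the rates that the annual report must judge are biased downward

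*Combined protocol and SAP*

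**What the plan says.** Section D, Imaging, gives the safety observation around the tracer: "Participants will be monitored visually and intermittently for adverse events during injection". The same paragraph has scanning continue to a whole-body acquisition 60 minutes after injection. The endoscopy paragraph of Section D describes needle cores taken through the whole gastric wall, in participants with diabetic gastroparesis (DG) only, up to 12 weeks from the scan. It mentions no later contact and no period over which adverse events are collected.

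Section F.5, Adverse Event Grading, defines what counts: "An adverse event is defined as either an expected side effect that is of a serious nature, or an unexpected side effect regardless of severity". It then sets the route into the record: "Any event that is reported to either the PI or his designated research associates by the subject or medical staff caring for the subject", provided the event meets that definition.

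The named risks are these:

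- **Biopsy, F.2.b item 3:** "Mild self-limiting serosal bruising and/or localized hematoma formation at the sites of EUS biopsies". Serious bleeding and perforation are put below 1 in 1000.
- **Biopsy, F.5 Expected risks:** "Adverse effects include abdominal pain, bleeding, and perforation", and "Rarely, these adverse events can lead to sepsis and death". Any serious adverse event is put at 1 in 2000 or less.
- **Tracer:** F.2.b item 2 says that "no adverse or clinically detectable pharmacologic effects were observed" in 17 subjects; F.5 adds that "there could be intolerance to the IV injection of radio ligand".

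Under F.5, Annual Review, the first question for the annual report is whether adverse event rates agree with what was assumed before the study.

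**The concern.** The plan commits itself to judging a rate but has no procedure that asks participants whether anything happened. The reporting deadlines (24 hours, or preferably 2 weeks), the quarterly review and the annual review in F.5 all act on events that someone has already reported. Two filters stand in front of them: an event must be brought forward unprompted, and if it is an expected effect it must also be serious.

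This matters more here than in a plain imaging study. The biopsy is a research procedure through the full gastric wall. The gastroparesis biopsy experience cited in F.1.c came from fine-needle aspiration, whereas this study takes cores. Sections C to F present the study as a pilot for larger work, so its own event counts will be carried forward. Section B lists abdominal pain among the cardinal symptoms of gastroparesis, and F.5 lists it as a biopsy effect. A participant may therefore put a change after biopsy down to her disease and not mention it unless asked.

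**Working it through.** The plan gives no safety sample size, threshold or target rate, so there is no figure of its own to reproduce.

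**1. Who is exposed and who is asked.** Section D plans 4 + 4 + 4 = 12 participants for PET, of whom the 4 with DG go on to biopsy. Scheduled safety enquiries after PET: 0 for 12. After biopsy: 0 for 4. The symptom questionnaire (PAGI-SYM) is described once, with no repeat after biopsy, so it does not fill the gap.

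**2. What the definition removes.** Abdominal pain is on the F.5 list of expected risks. Mild bruising and hematoma are named in F.1.c and F.2.b and so also read as expected. When not serious, neither is an adverse event under F.5, even if reported. F.5 also grades events as mild, moderate or severe, but under this definition the mild grade is left largely to unexpected events.

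**3. What zero events could show with complete capture.** The exact one-sided 95% upper limit for 0 events in n is 1 − 0.05^(1/n).

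- Tracer experience cited in F.2.b, n = 17: 1 − 0.05^(1/17) = 16.2%
- PET here, n = 12: 1 − 0.05^(1/12) = 22.1%
- Biopsy here, n = 4: 1 − 0.05^(1/4) = 52.7%

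**4. Against the assumed serious rates.** The number of event-free procedures needed to bring that limit down to a rate p is ln(0.05)/ln(1 − p): 2,995 for 1 in 1000 and 5,990 for 1 in 2000. With 4 biopsies at a true 1 in 1000, the chance of recording none is 0.999^4 = 99.6% with full capture and 0.9995^4 = 99.8% with half capture. For rare serious events, capture hardly changes the count in a study this small.

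**5. Illustration for commoner effects (assumed inputs).** The documents give neither a rate for mild effects nor the share s of events that unsolicited reporting captures. Take a true rate of 20% and range s. The chance of recording zero is (1 − 0.20 × s)^n:

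| s | n = 4 | n = 12 |
|---|---|---|
| 1.00 | 41.0% | 6.9% |
| 0.75 | 52.2% | 14.2% |
| 0.50 | 65.6% | 28.2% |
| 0.25 | 81.5% | 54.0% |

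This shows the direction and possible scale of the loss. It does not estimate the loss in this study. For expected non-serious effects the F.5 definition makes the loss complete whatever s is.

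**The case against.** The strongest reply is that sample size, not capture, is what limits the safety information. Safety is not an endpoint (Section D names biodistribution as primary), and 4 biopsies cannot test 1 in 1000 or 1 in 2000 however carefully events are sought. That stands: complete capture is needed for the limits in step 3 to be valid, but it does not make them narrow. The plan nowhere says that zero events would show safety, and a reader should not attribute that claim to it.

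Second, treating staff are a reporting route as well as the participant, and a plausible one for perforation, bleeding or sepsis. DG participants are also seen again if endoscopy follows on a later day. Both points are fair, but neither is a stated enquiry. Consent and contact pages are not in the public copy, so it would go too far to say that participants are never asked. Instructions to call in would still be unsolicited reporting.

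Third, two stronger readings are tempting and unsupported.

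- A reader might infer that entry on a GCSI of at least 3 selects for abdominal pain. As Section D describes the index, its subscales are nausea/vomiting, fullness/early satiety and bloating. The masking argument rests only on the general description in Section B.
- A reader might count injection intolerance among risks that appear late. The documents give no onset times, and this is the risk that observation during injection most directly covers. For bleeding, perforation and sepsis, later onset is a reasonable inference but is not documented either.

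Finally, calls that use a checklist of expected effects would leave the recorded rate for mild effects unchanged unless the F.5 definition also changes. That is correct, and the fix covers it.

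**Conclusion.** The concern holds as a problem of ascertainment. Stated observation covers the injection only, other events depend on unsolicited reports, expected non-serious effects are defined out, and nothing is scheduled after PET (12 participants) or biopsy (4). The annual comparison of rates therefore works from a count that can only be too low.

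The direction of the bias follows from the text; its size cannot be derived, because the capture share and the rate of mild effects are not given. The effect falls mainly on non-serious events. For serious events at the assumed rates, the expected count in 4 biopsies is at most 4/1000 = 0.004, so no method of capture would make the comparison informative. Even after correction, zero events would leave upper limits of 22% for PET and 53% for biopsy.

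The benchmark itself also needs attention. F.2.b bounds two specific complications at less than 1 in 1000, while F.5 bounds all serious events at 1 in 2000 or less. The part thus has a looser bound than the whole, and the annual review needs one stated assumption.

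**What to change.** In Section F.5:

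- State an adverse event collection window for PET and another for EUS biopsy.
- Add a scripted enquiry by the study coordinator after each procedure, using one checklist of the effects named in F.2.b and F.5 plus an open question, and asking about change from the participant's usual symptoms. The investigators should set the timing.
- Amend the definition so that expected non-serious events are also recorded, and can be reported separately from serious and unexpected ones.
- Report counts per procedure with exact confidence limits, and state that zero events would not establish safety at these sample sizes.
- Reconcile the two assumed serious-event figures in F.2.b and F.5.

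This changes data collection only; the length of clinical observation stays with the investigators. As a guide to cost, one contact after each PET scan and two after each biopsy makes 12 + 4 × 2 = 20 short calls plus one checklist. The downside is that more mild events will be recorded and the reported rate will look slightly less favourable.

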Image analyses: PET and CT images will be transferred to a dedicated workstation (MIM Software Inc., OH). Image analyses will be done by a board-certified nuclear radiologist. Diagnostic image quality of the late PET images will be rated on a 5-point Likert scale. Ratings of ≥ 3 will be considered acceptable for diagnostic use whereas ratings of 1-2 will be considered unacceptable. On each PET image, volumes of interest (VOIs) will be

Table 1: Enrollment criteria for DG and Diabetic patients

Inclusion criteria	Exclusion criteria

 -Female - Ability to provide informed consent - Age 18-70 years - Type I or II diabetes mellitus - Clinical gastric emptying testing within 6 months of study enrollment (for DG patients only) -Gastroparesis defined by gastric retention of Tc-99m >20% at 4 hrs on scintigraphy (for DG patients only) - Average Gastroparesis Cardinal Symptom Index (GCSI) ≥ 3 suggesting moderate-severe symptoms (for DG patients only) 	
 - Women who are pregnant or cannot stop breast feeding for 24 hrs - Using anti-coagulants, anti-inflammatory medications (NSAIDs, corticosteroids, etc.) or immunosuppressive therapies within 4 weeks prior (for DG patients only) - Opioid use within last 4 weeks of gastric emptying scintigraphy (for DG patients only) - Prior gastric surgery - History of IBD, celiac disease, eosinophilic gastroenteritis, microscopic colitis

drawn around the stomach and other organs that may show radiotracer accumulation. The uptake in each VOI in each PET image will be measured and decay-corrected to the time of injection and normalized to the administered activity. The quantified VOI activity for all PET images will be converted to time-activity curves, and the retention of activity in each region will be used along with the IF to model the biodistribution of ¹¹C-ER 176. The radiopharmaceutical biodistribution will also be quantified by standard metrics [maximum & mean standardized uptake value (SUVmax and SUVmean respectively)]. The image quality, time-activity curves, and semi-quantitative metrics will be compared between diabetic gastroparesis patients and controls.

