Upper endoscopy with endoscopic ultrasound and targeted biopsies of gastric muscle: A pregnancy test will be administered to women of child-bearing potential. Upper endoscopy will be performed only on DG patients only. The endoscopy will be performed within 12 weeks of the participant's PET/CT scan, this will allow more scheduling flexibility for the participant and study team. During the endoscopy procedure an additional procedure known as endotracheal intubation may be performed to keep the airway open and assist with breathing. This will vary from case to case and is determined by the anesthesiologist assisting with or the physician performing the endoscopy. The echoendoscope (Aloka Arietta 850; Olympus, Center Valley, PA) will be advanced into the gastric lumen and a site targeted for EUS-guided core biopsies based on findings of the PET scan. Fine needle biopsy of the gastric wall will be performed using a 19 G needle (SharkCore; Medtronic, Minneapolis, MN) passed through the echoendoscope and across the entire gastric wall ensuring a full thickness (mucosa to serosa) core tissue sample. Sampling of the uninvolvled region will be done to serve as control. In patients who do not have clear signal on PET/CT, sampling will be done from gastric antrum and body to act as negative control. All endoscopic procedures will be done by advanced endoscopist [REDACTED] [REDACTED]. EUS-guided core biopsy is a safe procedure associated with a low risk of adverse events.

Assessment of gastric macrophages: After tissue dissociation, using technique similar to that shown in the preliminary data, cells will be sorted and profiled using the Fluidigm (San Francisco, CA) Helios cytometry by time of flight (CyTOF) mass spectrometry system. After cleanup in FloJo to obtain singlets, data will be analyzed using the R-based CytofKit tool^{38, 39}. In an approach that was not biased towards a limited subset of cell types, cellular subtypes will be identified and counted after labeling with a panel of 32 antibodies to distinguish monocytes and tissue myeloid cells from the other immune cells (CCR2, CD24, CD64, Ly6C, CD115/CSF1R, CD38, CD8a, Ly6G, CD11b (Mac-1), CD3e, CX3CR1, MERTK, CD11c, CD4, ESAM, PDL-1, CD14, CD44, F4/80, PDL-2, CD161 (NK1.1), CD45, FcER1, SiglecH, CD19, CD45R (B220), I-A/I-E, SIRPa (CD172a), CD206 (Mrc1), CD62L, IL2RA, CD25, TER-119). Data will be displayed as tSNE maps and heatmaps.

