Endpoints and statistical analysis: The biodistribution of ¹¹C-ER 176 in the stomach using time activity curves and other described imaging metrics will be the primary endpoint. Correlative analysis will be done between biodistribution on ¹¹C-ER176 and pro-inflammatory markers on cellular expression using CyTOF. The proposed study will provide means and standard deviations for larger investigation in this area. Considering the robust expression of TSPO in gastric macrophages in our preliminary data, we expect to see uptake of TSPO ligand ¹¹C-ER 176 in the gastric muscle.

Anticipated results, potential pitfalls and alternative strategies: We anticipate finding that patients with DG will have significantly higher PET uptake of ¹¹C-ER176 compared to healthy volunteers. Additionally, we anticipate that the uptake will strongly associate with upregulation of TSPO and other pro-inflammatory markers like Ly6C and downregulation of anti-inflammatory markers like CCR2, CX3CR1 and CD206. Most second-generation TSPO radioligands have varying degrees of sensitivity to the single nucleotide polymorphism rs6971 in the TSPO gene⁴⁰, and this genotype sensitivity may vary depending upon the organ where it is expressed²². Therefore, some subjects who are low-affinity binders are excluded from analyses and the remaining subjects are corrected for being either high- or mixed-affinity binders. On the other hand, ¹¹C-ER176, a third-generation ligand, has shown little *in vitro* sensitivity to rs6971. However, *in vivo*, ¹¹C-ER176 was found to be sensitive to rs6971. Nevertheless, it allowed quantitation even in low affinity binders and had high non-displaceable binding potential, which suggests that its relative *in vivo* sensitivity to rs6971 may not impact clinical imaging²². Due to the small sample size of this feasibility study, we will be unable to select subjects with varying TSPO affinity genotype. However, if we see insufficient binding, we will determine the genotype.

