Subject Privacy: Data are kept in strict confidence. The template consent form required by Mayo Clinic's IRB includes appropriate language addressing the risks and confidentiality protection. Confidentiality is assured by the use of study number identifiers assigned to each participant. All data will be identified with the use of the study number identifier to the participant. Participants are assured protection of confidentiality as specified by the HIPAA language contained within the standardized template.

Data Confidentiality.

Database protection: The Mayo Clinic software programs are secured with password protection. All information kept within Excel spreadsheets use a study number identifier. Any electronic communication with collaborators outside the Mayo Clinic would include data identified by study number only. The only people with access to the spreadsheet are the study coordinator and the study statistician. The remaining investigators only review group data that have been summarized by the biostatistician.

Secure storage of biospecimens: Tissue samples collected are submitted to a designated laboratory technologist after anonymizing with a study number that is unrelated to the patient's Mayo Clinic registration number. Thus, the technologist does not have access to clinical information. The database that includes sample numbers and Mayo Clinic numbers is maintained in an Excel spreadsheet by the study coordinator.

G. Sharing Plan

We will share materials and manage intellectual property as described in the NIH Sharing Policies and Related Guidance on NIH-Funded Research Resources including the NIH Public Access Plan for Increasing Access to Scientific Publications and Digital Scientific Data from NIH Funded Scientific Research (February, 2015) and the NIH Genomic Data Sharing Policy (August, 2014).

Following publication, we will share our results, methodology, and reagents with the research community at large in a manner consistent with data/resource sharing policies of the National Institute of Health, the Mayo Clinic and the publishers of the journals where our reports will appear. Should any intellectual property arise which requires a patent, we will ensure that the technology (materials and data) remain widely available to the research community according to the NIH Principles and Guidelines document.

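### No masking of the image reader to group is stated, although drawn volumes and a subjective quality rating underlie the primary imaging metrics and the comparison of diabetic gastroparesis (DG) patients with controls

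*Combined protocol and SAP*

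**What the plan says.** Section D, Image analyses, names one reader: "Image analyses will be done by a board-certified nuclear radiologist". Two steps depend on that person's judgement or on how the software is steered. First, "Diagnostic image quality of the late PET images will be rated on a 5-point Likert scale", with a score of 3 or more counted as acceptable. Second, volumes of interest are "drawn around the stomach and other organs that may show radiotracer accumulation", and every time-activity curve and SUV is taken from them. The section ends: "The image quality, time-activity curves, and semi-quantitative metrics will be compared between diabetic gastroparesis patients and controls".

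Endpoints and statistical analysis says that stomach biodistribution "using time activity curves and other described imaging metrics will be the primary endpoint". The paragraph on anticipated results then gives the direction: "We anticipate finding that patients with DG will have significantly higher PET uptake", relative to healthy volunteers.

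The upper endoscopy paragraph has "a site targeted for EUS-guided core biopsies based on findings of the PET scan", and endoscopy is done in DG patients only.

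Section F.5, under Subject Privacy, says "Confidentiality is assured by the use of study number identifiers assigned to each participant". Under secure storage of biospecimens, it keeps clinical information from the laboratory technologist who handles tissue. It makes no such statement about the image reader.

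**The concern.** Where a contour is placed on a thin-walled organ, and how image quality is scored, can be influenced by what the reader expects to see. Here the expectation is written into the plan, and there are only 4 participants per group. One or two readings shaped by expectation could create, enlarge or hide a difference in group means. The plan intends those means and standard deviations to inform a larger study, so a distortion here would carry into that study's design.

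The biopsy step adds a specific route to unmasking. Because only DG patients have endoscopy, any PET read made to choose a biopsy site identifies the scan as DG. The plan sets no order between that read and the quantification.

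**Working it through.** **1. Is masking stated anywhere?** The places that could supply it are these.

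| Place | What it covers | Does it hide group from the image reader? |
|---|---|---|
| D, Image analyses | Reader, rating, volumes, comparison | Not stated |
| D, Endpoints and statistical analysis | Endpoint, correlative analysis | Not stated |
| F.5, Subject Privacy | Study numbers on all data | Not stated; given as confidentiality |
| F.5, Data Confidentiality | Spreadsheet limited to coordinator and statistician; other investigators see group summaries | Covers the spreadsheet, not the images on the workstation |
| F.5, biospecimen storage | Technologist has no clinical information | Tissue only |

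The plan also gives no contouring rule, reading order or time at which measurements are locked.

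**2. How sensitive is mean uptake to the contour?** The plan gives no figure to reproduce, so this is an illustration.

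Input from the plan: spatial resolution 3.7 mm (section D, Imaging), used as the FWHM, so sigma = 3.7/2.355 = 1.57 mm. Assumptions: wall thickness w of 3 to 5 mm, wall activity 1, background B of 0 or 0.3, and a one-dimensional profile.

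*Wall-only volume.* The blurred profile is p(x) = B + (1 - B)[Φ((x + w/2)/σ) - Φ((x - w/2)/σ)]. The ratio is the mean of p over width w + 2 mm divided by the mean over width w.

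| w (mm) | B | Mean, width w | Mean, width w + 2 | Ratio |
|---|---|---|---|---|
| 3 | 0 | 0.593 | 0.501 | 0.845 |
| 3 | 0.3 | 0.715 | 0.651 | 0.910 |
| 4 | 0 | 0.688 | 0.584 | 0.848 |
| 4 | 0.3 | 0.782 | 0.708 | 0.906 |
| 5 | 0 | 0.749 | 0.643 | 0.858 |
| 5 | 0.3 | 0.825 | 0.750 | 0.910 |

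A contour 1 mm wider per side lowers the mean by 9% to 16%.

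*Whole-stomach volume.* The walls and blur are the same, with an assumed 60 mm lumen and with lumen and outside tissue both at B. The outer edge moves out 1 mm per side.

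| w (mm) | Ratio, B = 0 | Ratio, B = 0.3 |
|---|---|---|
| 3 | 1.118 | 1.017 |
| 4 | 1.079 | 1.015 |
| 5 | 1.056 | 1.013 |

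The mean now rises, by about 1% to 12%. SUVmax does not change in either model if the volume already contains the peak, because the added tissue is less active.

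**3. What would a reader shift do to a comparison?** The plan specifies no test. Suppose a two-sample t-test at two-sided 5%, no true difference, and DG readings shifted by b standard deviations. The noncentrality is b/√(1/n1 + 1/n2). For 4 v 4 and b = 0.5 it is 0.5/√0.5 = 0.707, on 6 degrees of freedom with critical value 2.447.

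| b (assumed) | 4 v 4 | 4 v 8 (controls pooled) |
|---|---|---|
| 0 | 5.0% | 5.0% |
| 0.25 | 6.0% | 6.6% |
| 0.5 | 9.2% | 11.5% |
| 1.0 | 22.3% | 31.5% |

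Nothing in the documents links step 2 to a value of b in step 3.

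**The case against.** The strongest reply is that silence is not evidence of an unmasked read. Section F.5 already puts study numbers on all data, and the radiologist may well receive coded scans. That is fair. A reader might infer from the plan that the radiologist works knowing the group, but no section says so.

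Three other inferences go too far.
- **Manual contours.** The volumes are only said to be drawn, on a dedicated software workstation. Manual, semi-automatic and threshold methods all fit that wording.
- **The same reader targets the biopsy.** The endoscopy paragraph names nobody for that read, and the endoscopist could make it.
- **The 9% to 16% is the size of the bias.** It shows only how mean uptake responds to contour width. The sign reverses if the volume encloses the whole stomach, and a group difference arises only if contours shift differently between groups.

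The setting also limits the weight: this is a feasibility study with no formal test, alpha or power. That lowers the severity, but group means taken from readings shaped by expectation would still be biased. The study numbers do not close the gap, because the plan does not say that they conceal group from the reader.

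**Conclusion.** The point holds as a missing safeguard. The primary metrics pass through reader-dependent steps, the expected direction is declared, and no masking, reading order or lock is stated for the one reader. The plan does withhold clinical information from the tissue technologist.

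The size of any bias is unknown. The contour figures (-9% to -16% wall-only, +1% to +12% whole-stomach, SUVmax largely unaffected) rest on assumed wall thickness, background and lumen. The error rates rest on an assumed reader shift and an assumed test. They show that the endpoint is sensitive, not that it is biased.

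A reader might also infer that coded scans would remove the bias at no cost. The documents do not support that. The images themselves may hint at group, masking does not cure a single reader's measurement error, and the biopsy step requires some sequencing. The change is worth making because it is cheap and protects the main comparison.

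**What to change.** Add to section D, Image analyses:

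- The radiologist receives scans labelled by study number only, with group and clinical information withheld.
- DG, diabetic and healthy-volunteer scans are mixed in the reading queue as far as scheduling allows.
- For each scan, volumes, time-activity curves, SUVs and quality ratings are locked before group is revealed.
- Any PET read used to target biopsy is made only after that scan's quantification is locked. The same reader may do both.

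Fully random order across all 12 scans is probably not practical. Recruitment is planned over 7 months, and endoscopy must follow the PET scan within 12 weeks, so DG scans cannot wait for the last control. The lock therefore has to be scan by scan, in time for endoscopy. The design paragraph places endoscopy after the scan at the second visit, while the endoscopy paragraph allows 12 weeks. These passages must be reconciled so that the time available for the locked read is clear.

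The cost is coordinator coding of 12 scans and a two-step read. No additional reader is needed.
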